	measure (instrument, scale, source)	
(1) Strengths and Difficulties Questionnaire (SDQ; Goodman, 1999) parent report internalising problems scale, adolescent report externalising and internalising problems scales at 6 and 12 months.
 
(2) Parenting practices: Parenting Scale Adolescent version (PSA) parent report
 
(3) Adolescent prosocial behaviours – The Prosocial behaviour subscale of the SDQ (Goodman, 1999). Adolescents and parents report at 6 and 12 months.
 
(4) Adolescent peer relationships – The Peer Relationship Problem subscale of the SDQ (Goodman, 1999)
 
(5) Interparental outcome - Dyadic Adjustment Scale (DAS-7) is a 7-item measure (Sharpley & Cross 182; Hunsley et al., 2001)
 
(6) Parent mental health – the Kessler 6 (Kessler et al., 2003)
 
(7) Parent Wellbeing - The Warwick-Edinburgh Mental Well-being Scale (SWEMWBS; Tennant et al., 2007)
 
(8) Conflict Behavior Questionnaire (CBQ-20) (Robin & Foster, 1989)
 
(9) Child-parent relationship – the Closeness subscale of the Child-Parent Relationship Scale (CPRS, short form) measures (Pianta, 1995)

		
(10) Family functioning – the Family APGAR scale (Adapatability, Partnership, Growth, Affection and Resolve; APGAR; Smilkstein, 1978).
 
(11) Parent self-regulation – the Parenting Self-Regulation Scale is a 12-item parent-completed measure of parental-regulation (Tellegen et al., 2022).
 
(12) Out of home placement
 
(13) Adolescent antisocial behaviours - Self Report Delinquency Measure (SRDM; Smith & McVie, 2003)

--	--	---

Randomisation

Following baseline assessment, families will be randomised on a 1:1 basis to either the intervention (TEEN TRIPLE P and SAU) or control arm (SAU only) using stratified permuted block randomisation, stratifying by local authority. The randomisation will allocate families as a cluster, so that parents from the same family are in the same trial arm.

The randomisation list will be produced in advance and will use a block size of 4. Outcome assessors, the research team excluding the trial manager and those undertaking the process evaluation will remain blind to allocation.

The trial statistician responsible for analysing the data will be blind. Therefore, the senior trial statistician (co-PI [name]) will conduct the randomisation. The randomisation will be embedded within the study database.

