The Trial Manager will be responsible for allocation and informing participants and intervention practitioners of a participants' allocation by phone and secure file transfer.

Randomisation will be conducted using statistical software R (version 4.2.2 -2022-10-31 ucrt), using R package 'blockRand'.

Blinding

Due to the nature of the trial, participants and practitioners will not be blind to allocation arm. In addition, the Senior Trial Statistician (PI [name]), Trial Manager, and researchers completing qualitative interviews will not be blind to allocation. All other researchers, including the Trial Statistician responsible for analysing the data and researchers carrying out data collection, will be blind to allocation arm. If inadvertent unblinding occurs during contact with a participant, this will be recorded and reported to the Trial Manager. We do not foresee any circumstance where unblinding will be necessary.

Risk assessment

A trial risk assessment has been completed to identify the potential hazards associated with the trial and to assess the likelihood of those hazards occurring and resulting in harm. This risk assessment includes:

- The known and potential risks and benefits to human subjects
- How high the risk is compared to normal standard practice
- How the risk will be minimised/managed

This trial has been categorised as a low-risk trial, where the level of risk is comparable to the risk of standard care. A copy of the trial risk assessment may be requested from the Trial Manager. The trial risk assessment is used to determine the intensity and focus of monitoring activity.

Site and Investigator selection

This trial will be carried out at 6 participating sites within the UK. All sites who are interested in participating in the trial will be required to complete a registration form to confirm that they have adequate resources and experience to conduct the trial.

Before the site can begin recruitment a site /coordinator must be identified. The following documents must be in place and copies sent to the Trial email account (see contact details):

- Local Authority site approval to commence the trial
- Favourable opinion from the relevant Research Ethics Committee
- A signed Trial Agreement
- Current Curriculum Vitae and GCP training certificate of the site Principal Investigator (PI)
- Completed Site Delegation Log and Roles and Responsibilities document
- Full contact details for all personnel involved, indicating preferred contact

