Sample size calculations were conducted using the statistical software R version 4.1.2 (2021-11-01) using the package 'pwr' version 1.3.0.

Table 2: Sample size calculations

		PARAMETER
Minimum Detectable Effect Size (MDES)		0.35
Pre-test/ post-test correlations	level 1 (participant)	0.5
Intracluster correlations (ICCs)	level 1 (participant)	-
	level 2 (cluster)	0.5

		PARAMETER
Alpha ²		0.05
Power		0.9
One-sided or two-sided?		Two-sided
Average cluster size (if clustered)		1.5
Number of clusters ³	Intervention	137
	Control	138
	Total	275
Number of participants	Intervention	206
	Control	206
	Total	412

Recruitment and screening

Participant identification

There will be one pathway for recruiting participants in each Local Authority (site). Practitioners in services will identify potential CYP participants in their service. Potential parents and CYP participants will be provided with trial information (either physically, online or by post/email) including an information sheet, copy of the consent/assent forms and contact information for the University of Warwick project team. If the parents are interested in taking part or would like to discuss the trial further, they can directly contact the University of Warwick research assistant/trial manager. Alternatively, with the consent of the parent, the Local Authority can

² Please adjust as necessary for trials with multiple primary outcomes, 3-arm trials, etc., when a Bonferroni correction is used to account for family-wise errors.

³ Please state how the data is clustered, if there is any clustering (e.g. by delivery practitioner or setting).

provide the University of Warwick research assistant/trial manager with the parents' contact details and the research assistant will contact the family.

If the CYP (and parent/guardian if appropriate) are interested in taking part, an appointment will be arranged with a research assistant (via telephone or teleconference) and the following will be carried out:

- The trial will be explained in detail, including the randomisation and consent process. Research assistants will ensure that the participant has had sufficient time to consider the information in the information pack.
- Eligibility will be assessed.
- Consent to participate will be obtained from either:
- CYP parent/guardian alongside assent from CYP if CYP is under 16 years-of-age

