Intervention	Standard Teen Triple P (TEEN TRIPLE P). The programme involves parents attending 10 (1-hour) one-to-one sessions, where they learn practical strategies for how to manage their child’s problematic behaviour, promote healthy development, and improve the quality of the parent-child relationship. Sessions are delivered face-to-face, either in person or via video-conferencing. All parents will be invited to attend sessions.

SAP version history

Version	Date	Changes made and reason for revision
1.0	25-05-2023	Initial draft
1.1	10/07/2023	Addressing YEF reviewer comments. Added pilot sample size justification, additional effect size justification from protocol, and minor edit to add an alternative analysis. Other typos and minor edits also made.
1.2	15/08/2023	Addressing comments by YEF internal review.

ROLES AND RESPONSIBILITIES

Trial Statistician:	[name]		
Role:	Research Fellow/Trial Manager		
Date:		Signature:	
Senior Statistician:	[name]		
Role:	Assistant Professor in Applied Statistics / senior trial statistician		
Date:		Signature:	
Chief Investigator (s):	[name] / [name]		
Role:	Professor / Assistant Professor (CEDAR, University of Warwick)		
Date:		Signature:	
Other non-signatory contributor to the SAP:	[name]		
Role:	Head of Department, Professor, and Cerebra Chair of Family Research (CEDAR, University of Warwick)		

Table of contents

SAP version history	6
Table of contents	8
Introduction	9
Background	9
Study Materials	11
Statistical Principles	19
Study population	22
Analysis	26
References	39
SAP Deviation Log	41

Introduction

This statistical analysis plan provides guidelines for the final presentation and analysis for the Building Positive Relationships with your Teen: Evaluating the Teen Triple P Programme (Teen TRIPLE P trial). This plan, along with all other documents relating to the analysis of this trial, will be stored in the Statistical Analysis Master File electronically and/or in hard signed copy formats.

Background

Rationale and research question

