All participants (in both trial arms) will complete assessments at baseline (prior to randomisation), 6- and 12-months post-randomisation and will be given a choice of how these are completed. These assessments can be completed in a number of ways, face-to-face, online on a website, via telephone, via videoconferencing, or on paper via the post. Participants, parents/guardians, young people and key stakeholders will be invited to participate in semi-structured interviews to ascertain acceptability and their experience of

the parenting programme and being in the trial. We will interview a sample of those randomised to each arm of the trial.

Randomisation

Families will be randomised with equal probability to either the intervention or comparator arm using random permuted blocks (block size 4), stratified by local authority site. The statistician doing the analysis will be blind to the treatment allocation. As the families and practitioners are not blind to treatment allocation (as this would be impossible given the intervention), there is no issue in terms of predictability.

Sample size

Sample size calculations were conducted using R version 4.1.2 (2021-11-01), and the 'pwr' R package.

Parents/carers within the same family will be randomised to the same arm, making this a cluster RCT, given responses within the same family are potentially highly correlated. We might expect, based on our previous research with families and consultation with the TMG (Trial Management Group), an average cluster size within families of up to a maximum of 1.5 parents and a high degree of correlation among parents/carers from the same family, so also allow for an ICC=0.5 (Davé et al., 2008). Following Teerenstra et al. (2012), we also allow for a correlation between baseline and follow-up measures of primary outcome of $r=0.5$ (this is a conservative estimate based on published SDQ test-retest correlations between 0.74-0.84; Nowak et al., 2008). The sample size is then inflated to account for 20% of families being lost to follow-up at the 12-month post-randomisation follow-up time point.

Allowing for the above assumptions and an effect size to be detected of 0.35 with 90% power and a two-sided alpha of 0.05, a sample size of $N=412$ ($N_1=206$, $N_2=206$) is required.

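### A fixed, published block size of 4 within local authority leaves later allocations partly inferable in this open trial, contrary to the SAP, and the blind analyst's listed role must be reconciled

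*SAP*

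**What the plan says.** **Sequence.** Protocol, Randomisation: "Following baseline assessment, families will be randomised on a 1:1 basis", and "The randomisation list will be produced in advance and will use a block size of 4". SAP, Randomisation: "random permuted blocks (block size 4), stratified by local authority site". The SAP then notes that families and practitioners cannot be blinded and concludes that "there is no issue in terms of predictability".

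**Who finds families and who learns allocations.** Protocol, Participant identification: "Practitioners in services will identify potential CYP participants in their service". Protocol, Randomisation: "The Trial Manager will be responsible for allocation and informing participants and intervention practitioners" of the result. The Trial Manager also takes eligibility queries before randomisation (Protocol, Participants) and is one of those who may explain the trial before consent (Protocol, Informed consent).

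**Analyst.** Protocol, Randomisation: "The trial statistician responsible for analysing the data will be blind". Protocol, Blinding, and SAP, Randomisation, agree. The Blinding section also declares the Trial Manager unblinded. The SAP's Roles and responsibilities table gives the Trial Statistician's role as "Research Fellow/Trial Manager".

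**The concern.** The SAP's reasoning runs the wrong way. Open delivery is what reveals past allocations, and past allocations are what make a small fixed block readable. Knowing one's own arm afterwards does not remove the need to hide the next family's arm. Neither document says that the block size is withheld from sites.

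The stake is selection. Someone who can anticipate the next arm can, knowingly or not, influence which family comes forward or how an eligibility query is answered. Adjustment for baseline SDQ and local authority repairs this only in part. The primary outcome is reported by unblinded parents, so concealment and blind analysis are among the main protections left.

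The analyst's status matters because the SAP leaves choices open until data are seen: covariates added where imbalance is large, a fallback model if random-effect variance is insufficient, a change of link function or a transformation, and removal of ineligible randomised participants.

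**Working it through.** The documents give no figure for predictability. Their sample size is used here only for scale.

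**Scale.** With d = 0.35, 90% power and two-sided 0.05, n = 172 per arm. The design effect is 1 + (1.5 − 1) × 0.5 = 1.25, the baseline factor is 1 − 0.5² = 0.75, and 20% are lost. So 172 × 1.25 × 0.75 / 0.8 = 201.6, or 202 per arm and 404 in total, within 2% of the stated 412. Then 412 / 1.5 = 274.7, which gives the stated 275 families.

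**Block of 4 at 1:1.** There are 6 equally likely sequences. Assume an observer who knows the block size and sees every earlier allocation at the site in order.

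- *Certain allocations.* The fourth is always forced. The third is forced when the first two match, which happens in 2 of 6 sequences. The share is (0 + 0 + 1/3 + 1) / 4 = 1/3, or 275 / 3 ≈ 92 families.
- *Best guess* (choose the arm with more places left). The chances of being right are 1/2 for the first, 2/3 for the second, (1/3 × 1 + 2/3 × 1/2) = 2/3 for the third and 1 for the fourth. The mean is 2.833 / 4 = 70.8%, or about 195 of 275 families.

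**Pace.** The protocol expects about 6 parents per site per month. At 1.5 per family that is 4 families, roughly one block per site per month.

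**Effect of varying the block size.** This was simulated with 46 families per site (275 / 6) and an optimal guesser who knows the possible sizes but not their order. The mixed sizes are assumptions, not taken from the documents.

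| Blocks | Certain | Best guess right |
|---|---|---|
| 4 only | 31.9% | 70.3% |
| 4 and 6 | 5.6% | 69.0% |
| 4, 6 and 8 | 2.3% | 67.7% |

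The first row is slightly below the exact values because 46 is not a multiple of 4.

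**Possible bias, as an illustration only.** Assume that every certain slot was exploited and that the families placed in those slots differed between arms by 0.2 to 0.5 SD after baseline adjustment. The bias would be one third of that, 0.07 to 0.17 SD, against a target effect of 0.35. The documents give no basis for choosing a value in that range.

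**Analyst role.** Three statements stand side by side: the analysing Trial Statistician is blind (protocol and SAP), the Trial Manager is not blind (protocol), and the Trial Statistician's role includes Trial Manager (SAP). They cannot all be true as written. In addition, the protocol's Stakeholders and interests section has families randomised by the trial statistician, whereas its Randomisation and Baseline measures sections give this to the senior trial statistician.

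**The case against.** The strongest reply is that nobody at a site is shown to hold the full sequence.

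- The protocol says only that participants and intervention practitioners are told allocations. Referrers are case-holding social workers and edge-of-care teams, and the local authority is told the eligibility result.
- The Timeline plans 120 practitioners for 137 intervention families, about 1.1 each, and the Contamination paragraph expects different practitioners in each arm. One practitioner would see a fragment.
- After referral the university team takes consent, confirms eligibility and completes baseline. The senior statistician then randomises within the study database, so a referrer does not control the order in which families reach randomisation. Data collectors are blind.
- The contact log is meant to detect differential recruitment, and the SAP reports screening and reasons for non-recruitment by local authority.

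Most of this stands. A reader might infer that referrers learn every past allocation at their site and can work out the next one before choosing whom to refer. The documents do not say so. What survives is narrower. Fragments can still be shared within a site. The Trial Manager sees every allocation while also handling eligibility queries and possibly explaining the trial before consent. The log is completed by local authority staff, and it detects steering without preventing it.

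On the analyst, a reader might infer that the analysis is in fact unblinded. That too goes beyond the text. The conflict rests on a job title with names removed, and the protocol's Blinding section lists the two roles separately. The randomisation wording under Stakeholders and interests looks merely loose. The role line itself remains unexplained.

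**Conclusion.** The SAP's statement on predictability is wrong and should not stand. With one published block size of 4 within local authority, up to one third of allocations (about 92 of 275 families) could be known in advance, and up to 70.8% guessed correctly. Both figures assume knowledge of the block size and sight of every earlier allocation at the site in order. The only person the documents clearly place in that position is the Trial Manager. Central randomisation after consent and baseline, together with the contact log, reduces the risk without removing it. No actual steering is shown.

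On analyst blinding, the documents contradict themselves by role title. That calls for reconciliation and does not establish that the analyst is unblinded.

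**What to change.** 1. **Sequence.** For any unused slots, generate a new list with block sizes varying at random within local authority (for example 4, 6 and 8). Hold the sizes in a restricted document outside the protocol and SAP. The gain is the near-removal of certain allocations, to about 2%. Guessing stays at about 68%. The cost is a new list and a larger possible imbalance within a site at any moment: half the largest block, so 4 families instead of 2.
2. **Wording.** Delete the SAP sentence on predictability and state who learns allocations at each site.
3. **If recruitment has closed.** Planned randomisation ran from 01/08/2023 to 30/09/2024, so there may be no unused slots. In that case correct the sentence and report the fixed block size as a limitation.
4. **Analyst.** Confirm an analyst without allocation access. The protocol's evaluation team list names only one statistics lead, who is also a co-principal investigator, and the Blinding section declares the senior trial statistician, a principal investigator, unblinded. A replacement is therefore not obviously to hand. If none is available, withdraw the claim of blind analysis and lock the primary analysis script on dummy arm codes before the true codes are released.
5. **Consistency.** Align the Stakeholders and interests wording on who randomises with the Randomisation and Baseline measures sections. Items 2 and 5 cost only an edit.
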